4.2 Primary endpoint of the study

The primary endpoint of the study will be a comparison of the outcomes in terms of percentage reduction of the area of the wound treated with the EmoLED device versus the wound treated with SOC at W10, both the difference in the individual patient and within the entire group of 90 recruited patients.

4.3 Secondary endpoints

The following secondary endpoints were identified for this study:

1. Treatment safety.
2. Outcomes comparison in terms of the percentage reduction of the area of the wound treated with the EmoLED device versus the wound treated with SOC only within the ten-week observational period.
3. Evaluation of difference in healing time between the two areas.
4. Pain reduction (with pre-treatment assessment on a 0-10 VAS)
5. Depending on the patient's willingness to continue to go to the study site, the observation of any unhealed area(s) over the 10-week period can be extended until complete healing or up to 20 weeks.

5. ADVERSE EVENTS

Although the available information and the physical and performance characteristics of the device do not suggest the possibility of adverse events, this section of the protocol considers the possibility that such events might occur.

An Adverse Event (AE) is any unfavourable change in health, or side effect, or unexpected benefit that occurs in a subject involved in a clinical study while the patient receives the treatment or within a specified period of time following completion of the therapy, which may not necessarily have a causal relationship with such treatment or clinical trial. An adverse event may therefore be any unfavourable and/or unexpected sign or symptom (including abnormal findings in laboratory tests), or a disease or condition temporally associated with the use of a medicinal product (being investigated during the trial) or an investigational device, irrespective of whether or not it is related to such medicinal product or device (being investigated during the trial).

The morbidity of each subject will be monitored throughout the study period. Any signs exhibited by patients will be observed during each study visit; patients will be prompted to report possible symptoms through direct questioning; for example: "How have you been feeling since your last visit?". Moreover, subjects will also be encouraged to spontaneously report any adverse events that may occur during the Study.

Any clinically significant anomaly found during the Study will be monitored and observed until normalisation, or until it can be clinically explained.

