The purpose of this study is to evaluate the efficacy of the EmoLED device in promoting the healing of skin ulcers. As it is an innovative device, data relating to its use in humans has not yet been reported in the literature. A first pilot study investigated the use of the above-mentioned device on skin sampling areas in patients treated by the Centro Grandi Ustioni [Severe Burn Centre] of the AOUP (Azienda Ospedaliero-Universitaria Pisana [Pisana University Hospital]). This study demonstrated the clinical safety of the device as well as its non-inferiority compared to other types of advanced treatment.

This study will consider skin ulcers of various aetiologies. Depending on the size of the wound or the presence of multiple wounds, the EmoLED device will be used to treat either the whole wound or half of the wound.

How the treatment will be applied will be explained in detail below. However, in short, treatment with EmoLED consists of irradiating the wound (or part of the wound) for 60 seconds with the light emitted by the device. This treatment is used as an adjuvant to standard therapy.

This treatment does not interfere with other systemic therapies that may be being administered, nor does it involve any additional risk compared to SOC. The potential benefit is reduced healing time, with the consequent indirect benefits that this entails.

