4. STUDY DESIGN

4.1 General design

This clinical study will be a multicentre, prospective, controlled study, whose aim is to evaluate the clinical efficacy of a battery-powered portable device that uses blue LEDs.

As described in greater detail in the statistical analysis section, at least a 20% difference between treated and untreated wounds is expected to be observed in the same patient within the specified observation period.

For safety, the operator will be equipped with UV protection glasses. The housing of the device is made of biocompatible material that can be disinfected with detergents commonly used in hospitals in order to prevent contamination.

The device passed all safety tests (electrical, electromagnetic and photobiological) required by current regulations on medical devices, as well as a precise risk and usability analysis, and was found to be suited to the intended use.

The treatment, which is provided in addition to the patient's standard therapy, will be performed at each visit for 60 seconds on each 5-cm diameter sub-area of the selected wound or part of it.

Therefore, for multiple wounds, one will be treated with the EmoLED device and one will be selected as a control wound; very large wounds will be divided into two halves and one of the two will be the control wound. This will reduce any variability associated with randomised clinical trials (RCTs) on skin ulcer conditions.

4.1.1 Selection of the treatment area.

All wounds will be cleaned with saline solution and, if there is slough/black eschar, surgical debridement will be performed using a scalpel. Only at this point will treatment with the EmoLED device take place.

If a patient has more than one wound and all wounds at enrolment are found to have a **diameter of less than 5 cm**, the worst of the wounds will be treated entirely with the EmoLED device, whereas the others will serve as control wounds. Progression of all wounds will be evaluated over the ten-week study duration.

By contrast, if a wound at recruitment has a **diameter greater than 5 cm**, the wound will be divided into two halves along the longest side, and only one of the two halves will be treated. The other half of the wound will be dressed with a multi-layered sterile dressing. The division line between the two halves of the wound will be marked with a permanent marker, which will be reapplied at each visit, or whenever it begins to fade, to prevent loss of the reference marks.

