5.1 Serious Adverse Events

A Serious Adverse Event (SAE) is defined as any unfavourable medical event which, at any dose, results in one of the following:

- Leads to patient's death;
- May lead to a fatal outcome in the short term;
- Leads to subject's hospitalisation or prolonged hospitalisation;
- Causes significant or persistent disability/incapacity;
- Another significant medical event.

Significant medical events that do not lead to the patient's death, or are not life-threatening, or do not require hospitalisation, may nevertheless be considered serious adverse events when, based on appropriate medical judgement, they may pose a risk to the subject's health or may require medical or surgical intervention to prevent one of the *outcomes* described above.

Hospitalisation is defined as the subject's stay (usually for at least one night) in a hospital or Accident and Emergency Room for observation and/or treatment. When it is uncertain whether hospitalisation occurred or was necessary, the adverse event must be considered serious.

Hospitalisation for elective surgery or for *routine* clinical procedures that are not the consequence of an adverse event should not be considered an adverse event. If an unfavourable event is reported during the procedure, it must be reported as an adverse event; whether this is "serious" or "non-serious" will be decided based on the usual criteria.

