5.2 Reporting of Adverse Events and Serious Adverse Events

All adverse events reported by the subject or observed by the investigator or by a member of his/her *team* will be reported in the Serious Adverse Event Form. The following information must be collected for each adverse event:

- onset and resolution date and time (duration);
- seriousness (defined subsequently in the text);
- any required treatments or interventions adopted;
- *outcomes*;
- relationship to the product used in the trial (defined subsequently in the text);
- if the adverse event has caused the subject to withdraw from the Study.

All adverse events must be recorded using the accepted diagnoses, where possible. Any abnormal laboratory results, vital signs or abnormalities detected at the physical examination must not be recorded as adverse events if it is known that they are a symptom or sign of a syndrome or a diagnosis already reported as such. For example, ST-segment elevation detected by ECG and increased serum creatine phosphokinase are both known signs of myocardial infarction; therefore, they need not be reported if myocardial infarction was already reported as an adverse event. However, if both occur separately and no myocardial infarction was diagnosed, then this event must be reported as an adverse event.

Seriousness categories and the causal relationship of adverse events must be defined using the parameters listed below:

Seriousness:

| | |
|----------|---|
| mild | easily tolerated, does not hinder normal activities of daily living |
| moderate | partially hinders activities of daily living |
| serious | fully hinders all activities of daily living |

Relationship with the Study procedures:

Not related: the temporal relationship between the adverse event and the use of the Study product is such that a reasonable relationship between the two is very unlikely.

Possibly related: the adverse event occurs in a time sequence consistent with the start of use of the Study product, but it may also be attributed to the subject's clinical status or to the Study procedures/requirements.

Definitely related: the adverse event occurs in a time sequence consistent with the start of use of the Study product, disappears after its discontinuation and appears again when it is resumed.

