Adverse event reports will be collected, analysed and managed according to the criteria indicated in 5.2. The most appropriate statistical instrument will be chosen for analysis based on the number and type of adverse events reported.

2. Outcomes comparison as percentage reduction of the area of the wound treated with the EmoLED device versus the wound treated with SOC alone during the 10-week observation period.

Both the areas of the wound treated with the EmoLED device and those not treated with the EmoLED device, as measured on the required observation days, will be considered. A statistical analysis of paired data will be

performed using repeated measurements. In particular, both a comparison of the measurements obtained on different days, separately, and an analysis that will take into account the global trend over the observation period, will be performed.

Tests for data paired to pairs of measurements obtained on different observation days will be performed in the first case. These tests will be applied separately to the various days, evaluating any significant differences in both treated and untreated areas. The adopted statistical test will be either a parametric (t-test) or a non-parametric test (Wilcoxon signed-rank test) depending on the observed data distribution. The statistical significance will be corrected for multiple comparisons (e.g., given the possibility of a positive correlation between the identified measurements, Benjamini-Hochberg correction will be considered).

In the second case, the area under the curve (AUC) will be evaluated for each subject and in each area in order to obtain information on possible differences between changes in the treated and untreated areas of the wound. Either parametric or non-parametric paired data tests (depending on parameter distribution) will be performed in order to evaluate any differences in the trends of this parameter summarising the healing dynamics both in the treated and untreated areas.

The mean value observed in the remaining subjects will be used for both approaches if there is any missing data. A sensitivity analysis will be performed using both the best value and the worst value observed in the subjects.

3. Evaluation of the difference in healing time between the two areas.

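### The adverse-event definition admits an unexpected benefit, so favourable events can enter the non-serious adverse-event counts

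*Combined protocol and SAP*

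**What the plan says.** The general definition is in Section 5: "An Adverse Event (AE) is any unfavourable change in health, or side effect, or unexpected benefit that occurs in a subject". No causal link to treatment is required. The next sentence draws a consequence from it: "An adverse event may therefore be any unfavourable and/or unexpected sign or symptom". That sentence goes on to include abnormal laboratory findings, and diseases or conditions associated in time with use of the device.

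The definition of a serious event in Section 5.1 is narrower: "A Serious Adverse Event (SAE) is defined as any unfavourable medical event which, at any dose, results in one of the following".

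Section 5.2 lists what is collected for each adverse event and gives two scales. The first, headed seriousness, runs from mild to serious by hindrance to daily living; its lowest grade reads "easily tolerated, does not hinder normal activities of daily living". The second classes the relationship to the study product as not, possibly or definitely related.

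Treatment safety is the first secondary endpoint in Sections 4.3 and 6. For its analysis Section 6 says: "Adverse event reports will be collected, analysed and managed according to the criteria indicated in 5.2". The statistical method is to be chosen once the number and type of events are known.

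**The concern.** A safety count should measure harm. Here the definition that decides what is collected names one kind of favourable event outright, and the sentence after it lets in findings that are unexpected without being unfavourable. Nothing later in the plan removes such events before the safety analysis.

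At stake is how the non-serious adverse-event table can be read. Section 2 asks for safety reports because the device has no CE marking, so those reports should show harm cleanly. Section 6 places every patient in both the treated and the control group. There is therefore no separate group of untreated patients against which a patient-level event rate could be judged. If some entries are benefits, a reader of the table cannot tell how much of the count is harm. Sites that read the definition literally may also record differently from sites that read it in the usual sense.

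**Working it through.** The plan states no figure on this point, and no sample size, power or significance level depends on the adverse-event wording. The check is a comparison of the relevant sections.

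1. **Entry.** Section 5, first sentence: an unexpected benefit is one of three listed alternatives, so it qualifies without being unfavourable. Second sentence: with and/or, either property is enough alone, so an unexpected but favourable sign qualifies.

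2. **What counts as unexpected.** No section defines it. Section 4.1 gives an expected difference of at least 20% between treated and untreated wounds, which has no upper limit and is not a cut-off for calling one patient's result unexpected. Section 4.3 makes pain reduction an endpoint but gives no expected size. Section 3.1 requires wounds at least 8 weeks old, and the Section 5 definition applies to anything occurring in the subject, control wounds included. Whether rapid closure of such a wound is unexpected is left to each investigator.

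3. **Grading.** A benefit that hinders nothing fits only the mild grade in Section 5.2, where it looks the same as a mild harm.

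4. **Relationship.** The possibly related class needs a time sequence consistent with the start of use, with the patient's clinical status as another possible explanation. An improvement after the first treatment can meet that. The definitely related class requires disappearance on stopping and return on resuming, which is less likely to apply.

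5. **Follow-up.** Sections 5.3 and 5.4 follow open events until findings return to baseline, among other end-points. Return to baseline makes no sense as a target for an improvement.

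6. **Serious events.** Section 5.1 requires an unfavourable event, so a benefit cannot be classed as serious. Section 5.2 sends all adverse events to a form named for serious ones, but the classification still rests on 5.1.

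7. **Analysis.** Section 6 takes adverse-event reports as collected under 5.2. No step there filters out favourable events.

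For scale only: if a patient-level rate were reported on all 90 patients, one patient whose only recorded event was a benefit would add 1/90 = 1.1 percentage points. Five such patients would add 5/90 = 5.6 points and nine would add 9/90 = 10 points. The counts 1, 5 and 9 are assumptions, and a patient who also had a true adverse event would add nothing. The documents give neither an adverse-event rate nor a rate of unexpected benefit, so none of these is an estimate.

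**The case against.** The strongest answer is that the clause covers only an unexpected benefit, and healing is expected. The introduction says "The potential benefit is reduced healing time, with the consequent indirect benefits that this entails", and Section 4.1 says "at least a 20% difference between treated and untreated wounds is expected to be observed in the same patient". Wound-area reduction is the primary endpoint and the second secondary endpoint, healing time is the third and pain reduction the fourth. This stands. A reader might infer from the definition that healing, the effect the device is meant to show, is itself counted as an adverse event. The documents do not support that. Reaching it means reading *unexpected* as *larger than expected*, and the protocol sets no such threshold. The missing threshold also cuts the other way, because nothing stops an investigator from making that reading in an individual case.

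Second, the surrounding text is plainly about harm. Section 5 speaks of morbidity and of anomalies followed until they normalise, and 5.2 asks for accepted diagnoses where possible and for treatments required. The full second sentence concerns signs, symptoms, diseases and conditions, and a symptom that stops is not naturally any of these. This makes routine recording of benefits less likely. It does not cancel the first sentence, which names benefits expressly.

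Third, the consequences are limited. No safety hypothesis, event-rate threshold or stopping rule depends on the count. Section 6 considers the type of event and prescribes no pooled patient-level rate. Each record carries an outcome and a relationship, so a recorded benefit could often be recognised later. Any error would overstate harm rather than hide it. All of this stands and sets the size of the point, but sorting events after the data are seen is a poor substitute for a correct definition.

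**Conclusion.** The definition is wrong as written, in a limited way. Read literally, Section 5 admits favourable events that Sections 5.1 and 5.2 are not built to handle, and they can reach the non-serious counts analysed for treatment safety. Serious adverse events, the efficacy endpoints and the sample size are unaffected.

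A reader might go further and conclude that the safety endpoint is corrupted, or that its event rate must rise with efficacy. The documents do not show that. Contamination requires investigators to record benefits as adverse events, and nothing indicates how many would. The size of the effect cannot be estimated from the plan. The conclusion rests only on the wording, on the absence of a rule for *unexpected*, and on the absence of a step that removes favourable events before analysis.

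**What to change.** Three changes to the text:

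- In the first sentence of the Section 5 definition, delete the reference to an unexpected benefit.
- In the second sentence, replace the and/or construction so that it covers an unfavourable sign or symptom, whether expected or not.
- Add a statement that improvement in wound area or pain is recorded only as efficacy. Any other unexpected benefit is entered in the Notes section of the Case Report Form, which Section 3.3 already provides for information not foreseen, and is kept out of the adverse-event tables.

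The cost is two wording changes and one added statement, with no new data item, visit or analysis. No harm signal is lost: unfavourable events stay reportable whether or not they were expected, and the Section 5 requirement to follow clinically significant anomalies is untouched. If recruitment has begun, sites should be told of the change, and events already recorded should be checked for favourable entries before the safety tables are produced.

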5.1 Serious Adverse Events

A Serious Adverse Event (SAE) is defined as any unfavourable medical event which, at any dose, results in one of the following:

- Leads to patient's death;
- May lead to a fatal outcome in the short term;
- Leads to subject's hospitalisation or prolonged hospitalisation;
- Causes significant or persistent disability/incapacity;
- Another significant medical event.

Significant medical events that do not lead to the patient's death, or are not life-threatening, or do not require hospitalisation, may nevertheless be considered serious adverse events when, based on appropriate medical judgement, they may pose a risk to the subject's health or may require medical or surgical intervention to prevent one of the *outcomes* described above.

Hospitalisation is defined as the subject's stay (usually for at least one night) in a hospital or Accident and Emergency Room for observation and/or treatment. When it is uncertain whether hospitalisation occurred or was necessary, the adverse event must be considered serious.

Hospitalisation for elective surgery or for *routine* clinical procedures that are not the consequence of an adverse event should not be considered an adverse event. If an unfavourable event is reported during the procedure, it must be reported as an adverse event; whether this is "serious" or "non-serious" will be decided based on the usual criteria.

5.2 Reporting of Adverse Events and Serious Adverse Events

All adverse events reported by the subject or observed by the investigator or by a member of his/her *team* will be reported in the Serious Adverse Event Form. The following information must be collected for each adverse event:

- onset and resolution date and time (duration);
- seriousness (defined subsequently in the text);
- any required treatments or interventions adopted;
- *outcomes*;
- relationship to the product used in the trial (defined subsequently in the text);
- if the adverse event has caused the subject to withdraw from the Study.

All adverse events must be recorded using the accepted diagnoses, where possible. Any abnormal laboratory results, vital signs or abnormalities detected at the physical examination must not be recorded as adverse events if it is known that they are a symptom or sign of a syndrome or a diagnosis already reported as such. For example, ST-segment elevation detected by ECG and increased serum creatine phosphokinase are both known signs of myocardial infarction; therefore, they need not be reported if myocardial infarction was already reported as an adverse event. However, if both occur separately and no myocardial infarction was diagnosed, then this event must be reported as an adverse event.

Seriousness categories and the causal relationship of adverse events must be defined using the parameters listed below:

Seriousness:

| | |
|----------|---|
| mild | easily tolerated, does not hinder normal activities of daily living |
| moderate | partially hinders activities of daily living |
| serious | fully hinders all activities of daily living |

Relationship with the Study procedures:

Not related: the temporal relationship between the adverse event and the use of the Study product is such that a reasonable relationship between the two is very unlikely.

Possibly related: the adverse event occurs in a time sequence consistent with the start of use of the Study product, but it may also be attributed to the subject's clinical status or to the Study procedures/requirements.

Definitely related: the adverse event occurs in a time sequence consistent with the start of use of the Study product, disappears after its discontinuation and appears again when it is resumed.

In addition to being recorded in the Case Report Form (*CRF*), serious adverse events (SAEs), which include suspected unexpected serious adverse reactions (SUSARs), must be reported by the investigator on the "Serious Adverse Event Report Form". This form must be completed and sent to the Study Coordinator immediately, i.e. within 24 hours from the detection of the SAE by the research staff. The original must be sent and a copy stored at the trial site.

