3.3 Subject recruitment and screening

Enrollable patients will be selected by the Principal Investigator or his/her delegate based on the study inclusion and exclusion criteria. Once it has been verified that patients meet the study inclusion and exclusion criteria, the Principal Investigator or his/her delegate will ask the patients to consent to the use of the EmoLED device for treatment, after briefly explaining to them the key features of the device and the expected effect. If patients agree, they will enter the treatment phase. At the same time, patients will agree to return to the facility every week over the required observation period.

Patient registration in the identification register

Each trial site must keep a register of all subjects enrolled in the clinical trial and assign an identification code, an alternative subject identification or contact information. (UNI EN ISO 14155:2012 para. 6.5.2)

² In the event of multiple wounds, one wound will be treated with the EmoLED device and one will be chosen as the control wound; large wounds will be divided into two halves, one of which will be the control wound. This will reduce the variables associated with the inter-individual variability of skin lesions, thereby increasing the power of the test.

³ Pregnancy and breastfeeding will be verified based on the patients' declaration.

To comply with this specific requirement, the Principal Investigator will create, update and keep the Patient Identification Register.

The Patient Identification Register will contain the personal details of the patients who have given their consent to participate in the study, as well as the enrolment date and the patient code, comprising the acronym of the province of the facility followed by a three-digit sequential numerical code.

The patient code will be indicated in the Patient Case Report Form as Name (site ID code) and Surname (number) in order to create a database of photographic records.

Only the Principal Investigator and, at the discretion of the Principal Investigator, the members of his/her team will be aware of the identity of the patients enrolled in the study.

If a patient withdraws from the study, the Principal Investigator or one of his/her delegates will record the event in the Identification Register and on the Case Report Form and will archive everything.

Patient Enrolment Form

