6. STATISTICAL PLAN

Ninety subjects will be enrolled in this study. Each subject is part of both the control group and the treatment group.

Given that each patient will both receive the treatment and will also be a control subject, both groups will contain the same number of subjects, even if some of the subjects withdraw from the study. A comparative study of the subjects' demographic data and other baseline characteristics will also not be necessary as the two groups will be perfectly superimposable.

Treatment will be administered immediately after the cleaning and any necessary debridement of the complete wound. The area of the wound that should not be treated with the EmoLED device will be duly marked and covered with different layers of sterile dressing; this facilitates treatment standardisation and uniformity, thereby limiting any variability; it will also enable the treated, untreated and adjacent areas of each subject to be coherently defined.

The aim of the statistical analysis will be to establish the efficacy of the treatment with the EmoLED device; the significance ($p<0.05$) of any difference observed in the healing process between treated and untreated areas will be evaluated. Specifically, the primary endpoint of the study is the percentage reduction of the area of the wound treated with the EmoLED device versus the wound not treated with the EmoLED device at W10.

The secondary endpoints are:

1. Treatment safety.
2. Outcomes comparison in terms of the percentage reduction of the area of the wound treated with the EmoLED device versus the wound treated with SOC only within the ten-week observational period.
3. Evaluation of difference in healing time between the two areas.
4. Pain reduction (with pre-treatment assessment on a 0-10 VAS)
5. (OPTIONAL) Depending on the patient's willingness to continue to go to the study site, the observation of any unhealed area(s) over the 10-week period can be extended until complete healing or up to 20 weeks.

Estimation of sample size

The considerations underlying the choice of the model described below were drawn from a review of the literature on leg ulcer therapies and healing dynamics as well as on past clinical experience data obtained by the sites involved in the study with the treatment in question.

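### The items section 5.2 requires for each adverse event omit the area affected, so local events cannot be reliably assigned to the EmoLED or the control area

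*Combined protocol and SAP*

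**What the plan says.** The comparison is between areas within a patient. Section 6 states that "Each subject is part of both the control group and the treatment group". Footnote 2, printed under section 3.3, explains that with several wounds one is treated and one is chosen as control, while "large wounds will be divided into two halves, one of which will be the control wound".

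The list of secondary endpoints in section 4.3 opens with "1. Treatment safety", and section 6 repeats it. Neither adds a measure or a comparison.

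Section 5.2 sets the data to be recorded: "The following information must be collected for each adverse event". Six items follow:
- onset and resolution
- seriousness
- treatments or interventions
- outcomes
- relationship to the trial product
- "if the adverse event has caused the subject to withdraw from the Study"

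For the analysis of endpoint 1, section 6 refers back to the criteria in 5.2 and adds: "The most appropriate statistical instrument will be chosen for analysis". The choice is to depend on how many events are reported and of what type. Area appears neither in the collection list nor in the analysis text.

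**The concern.** Every patient is irradiated somewhere, so a count of patients with an event has no untreated group beside it. The one controlled safety question this design could address is whether local events occur more often in the EmoLED area than in the control area of the same patient. That requires knowing where each local event occurred, and no required item records it.

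Local events are foreseeable. Section 4.1.1 already provides for signs of wound infection, and section 1.1 describes a device that acts partly by warming tissue. Section 2 also gives the lack of CE marking as the reason for collecting safety reports. If the plan is followed as written, endpoint 1 may end as a list of events that cannot say whether the irradiated side fared worse.

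**Working it through.** **1. Is there a safety figure to reproduce?** No. The only computed figure in the plan is the primary-endpoint sample size. It reproduces exactly: with SD of the difference 50·√(2(1−ρ)), effect 20, one-sided α 0.05, power 80% and effective sample size 0.864·n in a noncentral t calculation, n = 83, 65, 47 and 29 for ρ = 0.1, 0.3, 0.5 and 0.7. It does not depend on this point.

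**2. Can any required or available item stand in for area?**

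| Source | What it gives | Why it does not supply area |
|---|---|---|
| Relationship to product (5.2) | The two lower categories rest on timing relative to use; the highest adds disappearance on stopping and return on resuming | Both areas share one patient and one calendar, so timing does not separate them; events in the control area are not counted |
| Accepted diagnosis, where possible (5.2) | Can separate wound events from systemic ones | In a divided wound both areas are halves of the same ulcer |
| Direct questioning (5) | The example is a general question about well-being since the last visit | It does not ask about either area |
| Photographs of both areas (4.1.2) | Visible changes | Named as a source for study outcomes, not for locating events; symptoms do not show |
| Notes section of the Case Report Form (3.3) | Free text | No location is required |

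**3. What can be estimated without area?** A patient-level rate only. For example, no events in 90 patients gives a one-sided 95% upper bound of 1 − 0.05^(1/90) = 0.033, or 3.3%, with no control rate to set against it.

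**4. What would area add?** The documents give no event rate, so the counts here are assumed and serve as illustration only. Suppose 9 of 90 patients have a local event, each in one area only. Without area, the result is 9/90 = 10%. With area, let b be the number with an event only in the EmoLED area and c the number only in the control area. The paired difference is (b − c)/90, with approximate standard error √(b + c − (b − c)²/90)/90.
- b = 8, c = 1: difference 7/90 = 7.8 percentage points; SE = √(9 − 49/90)/90 = 3.23 points; 95% interval 7.8 ± 1.96 × 3.23, or 1.4 to 14.1. Exact McNemar p = 2·(1 + 9)/2⁹ = 20/512 = 0.039.
- b = 5, c = 4: difference 1/90 = 1.1 points; SE = √(9 − 1/90)/90 = 3.33 points; 95% interval −5.4 to 7.6. Exact McNemar p = 1.0.

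The data that 5.2 requires cannot tell these two results apart.

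**5. How far would a test carry?** If all k discordant patients fall on one side, the two-sided exact p is 2·0.5^k: 0.0625 for k = 5 and 0.031 for k = 6. With five or fewer discordant patients the test cannot reach two-sided p < 0.05.

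**The case against.** A reader might infer that the trial cannot compare safety between the areas at all. The documents do not support that. The 5.2 list is a minimum, and the Case Report Form and adverse-event form are not among the documents, so either may hold a location box. Photographs of both areas, the doctor's entries and the diagnosis could place some visible events afterwards. What stands is narrower: the protocol does not require the item, and these sources cannot be relied on for symptoms or for two halves of one ulcer.

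A reader might also infer that the plan breaks a promise of a between-area safety test. It makes no such promise. The efficacy endpoints name a comparison; the safety endpoint does not, and section 2 speaks only of reports on safety and usability. The remark in the introduction that the treatment adds no risk over standard care is background, not a hypothesis. The argument for the change is therefore what the design could deliver cheaply.

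The strongest objection is that a by-area test would not be a clean comparison. Under section 4.1.1, when all of a patient's several wounds are below 5 cm, the worst receives EmoLED and the others are controls, so the areas differ at baseline. In divided wounds the halves share a boundary and a bandaged limb, so some events belong to both or to neither. No blinding of whoever would assign the area is described. All of this stands. It argues for a descriptive table with an interval rather than a decisive p-value, but it does not remove the need to record the area.

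Finally, section 5 expects practically no events, so any comparison may be imprecise. That also stands.

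**Conclusion.** The point holds for local wound events and for the data the protocol requires. Those data support only an uncontrolled patient-level rate for endpoint 1; other records could recover part of the missing information, but not reliably all of it. Systemic events remain uncontrolled in this design even with an area field.

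The size in this trial is unknown because no event rate is given. The 8-to-1 and 5-to-4 splits show what would be lost, not what to expect. The conclusion assumes that the unseen forms add no required location item; if they do, the remaining gap is the unspecified analysis. Efficacy conclusions and the sample size are untouched. The change is worth making before data are collected, because area cannot be dependably rebuilt later.

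**What to change.** 1. Add to the 5.2 list, and to the forms, a required field for area affected: EmoLED area, control area, both or boundary, not wound-related.
2. For endpoint 1 in section 6, pre-specify a within-patient tabulation of local events by area, with the paired difference and its confidence interval.
3. Use one designated control area per patient, fixed at enrolment. Footnote 2 speaks of one control wound and section 4.1.1 of all the others, so the text should say which one enters the table.
4. Show split-wound and separate-wound patients separately. In the latter the worst wound receives EmoLED, so an imbalance there cannot be attributed to the device alone.
5. Treat an exact McNemar p-value as optional and supportive only. List systemic events descriptively.

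The cost is one form field and one table. The drawback is low precision if events are few.
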